2.2.1. Nonclinical Studies of PF-07321332

Data from nonclinical studies support the planned clinical trials with PF-07321332; these studies are described in the IB.²⁶

PF-07321332 exhibits a broad-spectrum activity across the Coronaviridae family of 3CL proteases demonstrating its potential for antiviral efficacy.

In vitro, PF-07321332 inhibited SARS-CoV-2 viral-induced cytopathic effect in monkey kidney Vero cell assays. PF-07321332 exhibited antiviral activity against SARS-CoV-2 in dNHBE cells. Furthermore, PF-07321332 inhibited HCoV229E viral-induced cytopathic effect in human MRC-5 cells with no detectable cytotoxicity at the highest compound concentration tested.

Test article-related findings identified in the safety pharmacology studies included changes in locomotor activity and transient higher respiratory rate and minute volume in rats at the high dose, as well as minor and transient hemodynamic changes (increased blood pressure and decreased heart rate) at the high dose in cynomolgus monkeys. The potential effects on safety pharmacology parameters are monitorable in the clinic, and no correlated clinical signs or histopathological findings in the relevant organs were observed in the 14-day or 15-day repeat dose GLP toxicity studies in rats or monkeys. ECG data were also collected in the 15-day GLP monkey study and there were no test article-related changes in ECG parameters (HR, RR-, PR-, QRS-, QT-, QTc-intervals) or ECG morphology in that study.

2.2.2. Clinical Overview

C4671001 (NCT04756531) is an ongoing FIH single and multiple dose escalation study to evaluate the safety, tolerability, and PK of PF-07321332 in healthy adult participants. Preliminary data from this study collected as of 07 April 2021 (SAD) and 14 April 2021 (MAD) in a total of 31 participants who were randomized and treated with PF-07321332 or placebo indicate that the clinical safety profile of PF-07321332 appears to be acceptable at single doses up to 1500 mg alone and up to 750 mg administered with ritonavir (100 mg at -12h, 0h, 12h), and at repeated daily doses administered orally for 10 days of up to 500 mg PF-07321332 BID with 100 mg ritonavir BID.

Preliminary PK data on Day 1, Day 5 and Day 10 following multiple oral administration of PF-07321332/ritonavir 75/100 mg, 250/100 mg, and 500/100 mg BID suggest less than proportional increase in exposures at steady state. Multiple dosing over 10 days achieved steady state on Day 2 with approximately 2-fold accumulation. Day 5 and Day 10 exposure was similar at all doses.

Following single doses of PF-07321332 with and without ritonavir, all AEs were mild and none were considered treatment related. There were no obvious trends in, or association of, TEAEs with dose level of PF-07321332. Following multiple doses, the most commonly observed AEs by SOC were Gastrointestinal Disorders and Nervous System Disorders. Diarrhea was the most common reported AE, occurring in 4 participants across treatment groups. A total of 5 treatment related TEAEs were observed in Part-2:MAD.

Across treatment groups, blood TSH increased in 3 participants, and 2 participants reported dysgeusia. The 3 participants with elevated TSH results did not experience related clinical symptoms and the free T4 results remained within reference range. No SAEs or deaths were reported based on these preliminary safety data as of 07 April 2021 and 14 April 2021.

Current evidence indicates that the clinical safety profile of PF-07321332 is acceptable at single doses up to 1500 mg alone and up to 750 mg administered with ritonavir (100 mg at -12h, 0h, 12h), and at repeated daily doses administered orally for 10 days of up to 500 mg PF-07321332 BID with 100 mg ritonavir BID.

C4671005 (NCT04960202), a Phase 2/3, randomized, double-blind, placebo-controlled study in nonhospitalized symptomatic adult participants with a laboratory-confirmed diagnosis of SARS-CoV-2 infection, included participants 18 years of age and older with at least 1 risk factor for progression to severe disease and with a COVID-19 symptom onset of ≤ 5 days. The study excluded individuals with a history of prior COVID-19 infection or SARS-CoV-2 vaccination before the Day 34 visit. The primary efficacy endpoint was the proportion of participants with COVID-19 related hospitalization or death from any cause through Day 28.

In the analysis of the primary endpoint from all participants enrolled in Study C4671005, an 89% reduction in COVID-19-related hospitalization or death from any cause compared with placebo in participants treated within 3 days of symptom onset was observed. 0.7% of participants who received PF-07321332/ritonavir were hospitalized through Day 28 following randomization (5 of 697 hospitalized with no deaths), compared to 6.5% of participants who received placebo and were hospitalized or died (44 of 682 hospitalized with 9 subsequent deaths) ($p < 0.0001$). In a secondary endpoint, PF-07321332/ritonavir reduced the risk of hospitalization or death for any cause by 88% compared with placebo in participants treated within 5 days of symptom onset; 0.8% of patients who received PF-07321332/ritonavir were hospitalized or died through Day 28 following randomization (8 of 1039 hospitalized with no deaths) compared with 6.3% of patients who received placebo (66 of 1046 hospitalized with 12 subsequent deaths) ($p < 0.0001$). Treatment with PF-07321332/ritonavir was safe and well tolerated.

A prespecified interim analysis of Study C4671002, which included 45% of the trial's planned enrollment, showed that the novel primary endpoint of self-reported, sustained alleviation of all symptoms for 4 consecutive days, as compared to placebo, was not met. The key secondary endpoint of COVID-19-related hospitalization or death from any cause through Day 28 was also examined at the interim analysis, showing 0.6% of those who received PF-07321332/ritonavir were hospitalized following randomization (2 of 333 hospitalized with no deaths), compared to 2.4% of participants who received placebo and were hospitalized (8 of 329 hospitalized with no deaths).

This study, C4671002, is ongoing and participant-level treatment assignment remains blinded.

2.3. Benefit/Risk Assessment

More detailed information about the known and expected benefits and risks and reasonably expected AEs of PF-07321332 may be found in the IB, which is the SRSD for this study. The SRSD for ritonavir is the USPI ²⁷ for NORVIR.

2.3.1. Risk Assessment

Potential Risk of Clinical Significance	Summary of Data/Rationale for Risk	Mitigation Strategy
Study Intervention(s) PF-07321332		
Emesis	Sporadic emesis was observed at ≥ 100 mg/kg/day of PF-07321332 in the 15-day NHP toxicology study.	AEs will be monitored and participants may receive antiemetics.
Hypertension	Transient increases in systolic, diastolic, and mean blood pressure were observed in the preclinical studies. In Study C4671005 (adults at high risk for severe disease), a small imbalance in 9 participants with reported events of hypertension was reported (1% vs <1%).	Vital signs will be monitored per SoA during the study during any in-clinic visits. All AEs will be monitored in the study. Concomitant medications will also be reviewed for potential new AEs and worsening of the condition.
Study Intervention(s): Ritonavir		
Gastrointestinal disturbances (including diarrhea, nausea, vomiting and abdominal pain)	Frequently reported adverse reaction in HIV-positive patients who are HIV-positive at 600 mg BID.	Lower dose of 100 mg twice daily is used in this study. There will be close observation of AEs. In addition to ongoing review of AEs by the sponsor, an E-DMC will review safety data as described in Section 10.1.5.1. Taking study intervention with food may improve tolerability.
Neurological disturbances (eg, paresthesia, including oral paresthesia, dysgeusia and dizziness)	Frequently reported adverse reaction in patients who are HIV-positive at 600 mg BID.	Lower dose used in this study. There will be close observation of AEs. In addition to ongoing review of AEs by the sponsor, an E-DMC will review safety data as described in Section 10.1.5.1.
Rash (most commonly reported as erythematous and maculopapular, followed by pruritic)	Frequently reported adverse reaction in patients who are HIV-positive at 600 mg BID.	Lower dose used in this study. There will be close observation of AEs and monitoring through targeted physical exams. If needed, therapeutic interventions per SoC may be provided.
Fatigue/Asthenia	Frequently reported adverse reaction in patients who are HIV-positive at 600 mg BID.	Lower dose used in this study. There will be close observation of AEs. Fatigue (low energy or tiredness) will be assessed through collection of

Potential Risk of Clinical Significance	Summary of Data/Rationale for Risk	Mitigation Strategy
		daily signs and symptoms and will also be assessed through targeted physical examinations when performed during the study visits.

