10.3.1. Definition of AE

AE Definition

• An AE is any untoward medical occurrence in a patient or clinical study participant, temporally associated with the use of study intervention, whether or not considered related to the study intervention.• Note: An AE can therefore be any unfavorable and unintended sign (including an abnormal laboratory finding), symptom, or disease (new or exacerbated) temporally associated with the use of study intervention.

Events Meeting the AE Definition

• Any abnormal laboratory test results (hematology, clinical chemistry, or urinalysis) or other safety assessments (eg, ECG, radiological scans, vital sign measurements), including those that worsen from baseline, considered clinically significant in the medical and scientific judgment of the investigator. Any abnormal laboratory test results that meet any of the conditions below must be recorded as an AE:
• Is associated with accompanying symptoms.• Requires additional diagnostic testing or medical/surgical intervention.• Leads to a change in study dosing (outside of any protocol-specified dose adjustments) or discontinuation from the study, significant additional concomitant drug treatment, or other therapy.• Exacerbation of a chronic or intermittent preexisting condition, including either an increase in frequency and/or intensity of the condition.• New condition detected or diagnosed after study intervention administration, even though it may have been present before the start of the study.• Signs, symptoms, or the clinical sequelae of a suspected drug-drug interaction.• Signs, symptoms, or the clinical sequelae of a suspected overdose of either study intervention or a concomitant medication. Overdose per se will not be reported as an AE or SAE unless it is an intentional overdose taken with possible suicidal/self-harming intent. Such overdoses should be reported regardless of sequelae.

Events **NOT** Meeting the AE Definition

- Any clinically significant abnormal laboratory findings or other abnormal safety assessments that are associated with the underlying disease, unless judged by the investigator to be more severe than expected for the participant's condition.
- The disease/disorder being studied or expected progression, signs, or symptoms of the disease/disorder being studied, unless more severe than expected for the participant's condition.

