6.2.9. Duration of Each Targeted COVID-19 Sign/symptom

Duration of each targeted COVID-19 signs/symptoms is defined as (First Date when the symptom alleviated/resolved) – (First Dose Date) +1 for each participant with baseline severity of mild, moderate, or severe.

For duration of each targeted COVID-19 sign/symptom, a Kaplan-Meier analysis providing the median and quartiles will be provided for each treatment group for mITT1 population set. Two additional figures (Number of Participants and Median Time to Sustained Alleviation of Each Targeted Sign/Symptom by Treatment Group [mITT1]) will be included for the endpoint of Duration of Each Targeted COVID-19 Sign/Symptom.

6.2.10. Progression to a Worsening Status in 1 or More Self-reported COVID-19 Associated Symptoms through Day 28

Participants will record a daily severity rating of their symptom severity over the past 24 hours based on a 4-point scale in which 0 is reported if no symptoms were present; 1 if mild; 2 if moderate; and 3 if severe.

Vomiting and diarrhea will each be rated on a 4-point frequency scale where 0 is reported for no occurrence, 1 (mild) for 1 to 2 times, 2 (moderate) for 3 to 4 times, and 3 (severe) for 5 or greater.

Progression to a worsening status for any targeted symptom will be derived programmatically based upon increasing severity (ie, the first time any targeted symptom worsens after treatment relative to baseline):

Progression to worsening (Yes/No)	
Increasing severity	Yes
Not increasing severity	No

The proportion of participants with progression (increasing severity for any targeted symptom) will be summarized by treatment group. Treatment comparison between groups will be presented as odds ratios with 95% CIs and p-value based on logistic regression model. The analyses will be done using mITT1 population. Missing severity at baseline will be treated as mild.

The above definition of worsening was derived only from participant diary data, to align the worsening with the primary and keys secondary endpoint, an expanded evaluation of

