6.6.1. Adverse Events

All adverse events will be coded according to the Medical Dictionary for Regulatory Activities (MedDRA) and will be summarized by treatment group within SAS population. Only TEAE summaries to AEs that started on or prior to Day 34 will be summarized. A list of pre-specified AESIs is provided in [Appendix 5](#).

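### Fatigue is a listed ritonavir risk to be followed partly through the daily diary, but no visible SAP analysis compares diary fatigue between arms, so drug-related fatigue is at risk of under-reporting

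*Protocol*

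**What the plan says.** - Protocol 2.3.1 has a ritonavir row headed "Fatigue/Asthenia". Its mitigation column gives the lower dose and close observation of AEs, then states: "Fatigue (low energy or tiredness) will be assessed through collection of" "daily signs and symptoms and will also be assessed through targeted physical examinations when performed during the study visits".
- Protocol Appendix 9 and SAP Appendix 4 carry the same symptom table. Fatigue is marked for study entry and for daily collection, but not as a targeted symptom for analysis.
- The SAP diary analyses are written on targeted symptoms. On worsening, SAP 6.2.10 says: "The proportion of participants with progression (increasing severity for any targeted symptom) will be summarized by treatment group".
- Protocol 10.3.1 lists among events that do not meet the AE definition: "The disease/disorder being studied or expected progression, signs, or symptoms of the disease/disorder being studied, unless more severe than expected" for that participant's condition.
- SAP 6.6.1: "All adverse events will be coded according to the Medical Dictionary for Regulatory Activities (MedDRA) and will be summarized by treatment group within SAS population". SAP 6.2.1 gives the treatment-emergent AE tables by system organ class and preferred term.
- Protocol 8.3.7, the section reserved for disease-related events that do not qualify as AEs, is marked not applicable.

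**The concern.** Fatigue is both a symptom of the disease and a named risk of the drug. The plan collects a patient-reported fatigue score before the first dose and every day to Day 28, under blinding and randomisation, and the risk table relies on that collection. The analysis plan then leaves the item unused. The reported evidence on fatigue as a harm would rest on AE counts, which depend on an investigator deciding, participant by participant, whether fatigue in someone with COVID-19 exceeds what the illness explains. An excess in the active arm could be diluted or missed although randomised data bearing on it exist. These are low-risk participants, so tolerability carries real weight in the benefit-risk judgement.

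**Working it through.** The plan states no figure on this point, so the check is mainly a tracing exercise.

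1. **Symptom table.** Items collected daily: 14. Items marked as targeted: 11. Difference: 14 − 11 = 3, namely fatigue, loss of smell and loss of taste.

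2. **Visible diary analyses in the SAP, by symptom set.**
   - Sustained alleviation (6.1.1.1): targeted.
   - Severe symptoms, and the per-symptom proportions and plots (6.2.7): targeted.
   - Sustained resolution (6.2.8): targeted.
   - Duration of each symptom (6.2.9): targeted.
   - Worsening (6.2.10): targeted. The endpoint title speaks more broadly of COVID-19-associated symptoms, but the derivation narrows it.

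   Analyses using the fatigue item: 0. Diarrhea, nausea and vomiting, also listed as ritonavir risks, are targeted and so do get diary results by arm.

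3. **Other routes for fatigue.**
   - *Safety section.* SAP 6.6 lists AEs, laboratory data, vital signs, discontinuations and treatment duration. It lists no diary data.
   - *Physical examination.* Protocol 8.2.3 requires cardiopulmonary assessment as a minimum and treats findings as source data, to be reported only if they meet the AE definition. Protocol 9.3.5.2 mentions a descriptive summary of examinations by arm, but SAP 6.6 has no such output.
   - *Treatment-emergent AEs.* Any recorded fatigue AE is tabulated by preferred term. Recording is filtered by 10.3.1, and because fatigue is a qualifying entry symptom, ordinary fatigue can reasonably be put down to COVID-19.
   - *Persistent symptoms.* Protocol 9.3.5.3 looks at Weeks 12 and 24, long after a 5-day course.

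4. **Would a diary table be informative?** This gives the precision of the table proposed below, not the size of any under-reporting. Take n = 1880/2 = 940 per arm (Protocol 9.5), with complete diaries. The control rates of new or worsened fatigue are assumed, since the documents give none.
   - SE = √{[p0(1 − p0) + p1(1 − p1)]/n}; half-width = 1.96 × SE; power ≈ Φ(0.05/SE − 1.96) for a 5-point excess.
   - p0 = 10%, p1 = 15%: SE = √(0.2175/940) = 0.01521. Half-width 2.98 points. Power Φ(3.287 − 1.96) = 0.908.
   - p0 = 20%, p1 = 25%: SE = √(0.3475/940) = 0.01923. Half-width 3.77 points. Power Φ(2.60 − 1.96) = 0.739.

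   Missing diaries would widen these intervals. The documents give no completion rate.

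**The case against.** The strongest reply is that the documents do not contradict each other. The sentence in 2.3.1 is a mitigation measure and promises collection, not a comparison by arm. Collection is planned, site staff review the diary at Days 5, 10, 14, 21 and 34 and at early termination, and the E-DMC sees unblinded safety data up to weekly. Protocol 8.3.1.2 requires all observed and spontaneously reported AEs on the CRF, and the safety objective is only descriptive. This stands as far as it goes: it is an omission from the analysis, not a broken promise. Staff review and E-DMC monitoring do not, however, put a fatigue comparison in the report.

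A second reply is that a diary comparison cannot isolate drug harm. Protocol 2.3.2 expects the drug to shorten and lessen symptoms, so less illness fatigue could offset drug-induced fatigue. Also, anyone scoring 3 on Day 1 cannot worsen on a 0-3 scale. Both points stand and shape the fix.

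Third, parts of the SAP (3.3, 6.3 and an Appendix 1 row) and of Protocol 9.3 are blacked out. The SAP version history names only Week 12 and Week 24 symptom analyses as added to 6.3, but a list of changes is not a full table of contents. The claim must stay limited to the visible text.

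**Conclusion.** The point holds for fatigue. A named drug risk has relevant diary data and no visible by-arm analysis of them through Day 28, and the AE tables that remain are open to under-ascertainment. The size is unknown and cannot be derived from the documents. The conclusion assumes that the redacted sections hold no such analysis. It affects no primary or key secondary result, but it is worth correcting because the remedy is cheap.

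Two stronger readings are tempting and not supported:

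- *Fatigue harms will go unreported, or sites are told to suppress them.* A reader might infer this from the 10.3.1 exclusion. But the exclusion lets through fatigue more severe than expected, and whatever is recorded is tabulated by arm and preferred term. Risk of under-reporting is as far as the text goes.
- *Taste disturbance has the same gap.* It is listed under "Neurological disturbances (eg, paresthesia, including oral paresthesia, dysgeusia and dizziness" and the diary has a taste item. But 2.3.1 relies there on AE observation, sponsor review and E-DMC review, with no mention of the diary. Dysgeusia is not in the COVID-19 symptom table, so the exclusion does not clearly reach it. The diary item asks whether taste is reduced or absent, not altered.

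**What to change.** 1. In SAP 6.6, add one descriptive table in the Safety Analysis Set from the existing diary. By arm, give the number and percent whose fatigue score exceeds their Day 1 score on Days 2-6 and on Days 7-28, with the risk difference and 95% CI. Place it beside the treatment-emergent AE rows for fatigue and asthenia.
2. Show the same results by Day 1 fatigue score, so that participants with no room to worsen are visible. State how missing Day 1 and later scores are handled, since the SAP's rule of treating missing baseline severity as mild was written for efficacy.
3. Add a footnote that the comparison is a net effect, drug harm less any symptom benefit, so a null or favourable result does not exclude harm, and that AE counts for these terms are subject to the 10.3.1 exclusion.
4. Reconcile Protocol 8.3.7 with 10.3.1.
5. A loss-of-taste row is optional. If included, note that it does not measure altered taste.

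Cost: SAP wording, one table and one reconciled protocol section. No new data, no formal test and no change to any efficacy analysis.

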2.3.2. Benefit Assessment

PF-07321332 has been shown to have SARS-CoV-2 antiviral activity in vitro and is intended to reduce virus titers, thereby reducing the duration and severity of symptoms and the risk of mortality in SARS-CoV-2 infected patients. Efficacy, safety and tolerability of PF-07321332 was demonstrated in the C4671005 study in adults at increased risk of progressing to severe COVID-19 illness. As a result, emergency use authorization has been granted for PF-07321332/ritonavir by the FDA for the treatment of mild to moderate COVID-19 in certain adults and pediatric patients (12 years of age and older) with positive results of direct SARS-CoV-2 testing, and who are at high risk for progression to severe COVID-19, including hospitalization or death. As noted in Section 2.2.2, at the 45% interim analysis for Study C4671002, a reduction in the number of hospitalizations or death was noted in participants treated with PF-07321332/ritonavir compared with placebo. On this basis, the potential benefit to individual study participants who receive the study intervention may include a shorter time to clinical recovery, prevention of hospitalization, and a lower probability of progressing to more severe illness or death. The potential benefit of the study is that it may provide a new treatment option for nonhospitalized patients with COVID-19 who are at low risk for progression to severe disease and hospitalization. In the context of the global pandemic public health emergency this treatment could play an important role in alleviating current pressures on health care systems globally.

2.3.3. Overall Benefit/Risk Conclusion

Taking into account the current COVID-19 global pandemic and the high burden of both mortality and morbidity and the potential for future epidemic outbreaks, the lack of readily available outpatient treatment options, and the measures taken to minimize risk to participants in this study, the potential risks identified in association with PF-07321332 are justified by the anticipated benefits that may be afforded to participants with COVID-19. An independent E-DMC will be responsible for monitoring the safety of participants at regularly scheduled intervals throughout the duration of the study and for assessing efficacy, futility and sample size estimation at the time of the interim analysis according to the E-DMC charter.

